## **11.1. Endpoints**

### **11.1.1. Primary Endpoints**

- Adverse events, collected until the 42-day post-last vaccination (excluding third vaccination) visit.
- Serious adverse events and IREs, collected from signing of the ICF onwards until the end of the study.
- Solicited local and systemic adverse events (reactogenicity), collected until 7 days after each study vaccine administration.

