#### *Safety and tolerability (Cohort 1 substudy)*

- Adverse events, collected from the day of the third vaccination onwards until 28 days thereafter (note: events that started before the third vaccination but are still present at the time of third vaccination should also be recorded).
- Serious adverse events and IREs, collected from signing of the original ICF onwards until the end of the study (including Cohort 1 substudy).

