Regimen*	Post-dose 1	Date and time of Dose 1 administration	Minimum of: a) 23:59 on the date of last contact (for early study discontinuations) b) 23:59 on the date of relative Day 29 Post-dose 1 c) one minute prior to Dose 2 administration d) 23:59 on the date of database cut-off (in case of interim analysis)
Post-dose 1 FU		One minute after the end of the Post-dose 1 period	Minimum of: a) 23:59 on the date of last contact (for early study discontinuation or completion) b) one minute prior to Dose 2 administration c) 23:59 on the date of database cut-off (in case of interim analysis)
Regimen*	Post-dose 2	Date and time of Dose 2 administration	Minimum of: a) 23:59 on the date of last contact (for early study discontinuation or completion) b) 23:59 on the date of relative Day 29 Post-dose 2 c) 23:59 on the date of database cut-off (in case of interim analysis) Note: subjects who do not receive Dose 2 will not have a Post-dose 2 period.
Post-dose 2 FU		One minute after the end of the Post-dose 2 period	Minimum of: a) 23:59 on the date of database cut-off (in case of interim analysis) b) 23:59 on the date of last contact (for early study discontinuation or completion)
Regimen*	Post-dose 3	Date and time of Dose 3 administration	Minimum of: a) 23:59 on the date of last contact (for early study discontinuation or completion) b) 23:59 on the date of relative Day 29 Post-dose 3 c) 23:59 on the date of database cut-off (in case of interim analysis) Note: subjects who do not receive Dose 3 will not have a Post-dose 3 period.

Post-dose 3 FU		One minute after the end of the Post-dose 3 period	Minimum of: a) 23:59 on the date of database cut-off (in case of interim analysis) b) 23:59 on the date of last contact (for early study discontinuation or completion)
-------------------	--	--	---

Note 1: * Regimen period includes both the Post-dose 1, Post-dose 2 and Post-dose 3 periods.

Note 2: FU = follow-up.

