7. SAFETY

The safety and tolerability data include the following:

- AEs collected from signing of the informed consent form (ICF) onwards until the 42-day post-last vaccination (excluding third vaccination) visit.
- AEs collected from the day of the third vaccination onwards until 28 days thereafter (note: events that started before the third vaccination but are still present at the time of third vaccination will also be recorded).
- Serious adverse events (SAEs) and immediate reportable events (IREs) from signing of the ICF onwards until the end of the study.
- Solicited local and systemic AEs (reactogenicity) recorded during the first 8 days (including the day of the vaccination) following each vaccination.

The safety and tolerability data will be summarized based on the full analysis set. The analysis will be based on the actual dose (ie, Dose 1, Dose 2 and Dose 3 for the first, second and third vaccination, respectively) that the subjects received. For example, if Dose 2 is not administered to a subject, then that subject will not be included in the analysis of AEs in the Post-dose 2 period. Focus will be on safety signals detected during the Post-dose 1, Post-dose 2 and Post-dose 3 periods, as well as the Regimen phase.

In general, safety data will be evaluated separately for each cohort. Within each cohort, the data will be presented by vaccination schedule.

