7.1.3. Analysis Methods

In general, the AEs following vaccination will be summarized (ie, tables of descriptive statistics) by vaccination schedule and presented per period/phase. Similar summary tables will also be provided pooled by vaccine (dose).

Furthermore, unsolicited AEs will be summarized (showing number and percentage) by System Organ Class (SOC) and Preferred Term (PT). Solicited AEs (recorded by day) will be converted into the analysis format of unsolicited AEs (recorded by event) as detailed in Attachment 2. These solicited AEs will be summarized by class (local, systemic) and Preferred Term. For solicited as well as unsolicited AEs, tables focusing on severity will be created. Focus will also be on the relationship (to the study vaccine) of the solicited systemic and unsolicited AEs.

The SAEs, AEs with fatal outcome, AEs leading to permanent discontinuation from study vaccination, Grade 3 AEs and IREs will also be listed. A table summarizing all those parameters will further be created and presented per analysis period and vaccination schedule. Summary tabulations by SOC and PT for each of the category of events (ie, SAEs, AEs with fatal outcome, AEs leading to permanent discontinuation from boost vaccination, Grade 3 AEs and immediate reportable events) will also be generated on the entire reporting period. Subject narratives will be generated for these events, except Grade 3 AEs. For Grade 3 AEs, the narratives will only be generated for those AEs that are considered related to study vaccination.

For the solicited local and systemic AEs, the duration and time to first onset of the events will also be summarized. If a subject experiences more than 1 occurrence of a solicited event, the maximum duration of the events will be used. The time to first onset is defined as:

$$[\text{date of first onset} - \text{reference date} + 1]$$

The reference date is the start date of each vaccination period (ie, Post-dose 1, Post-dose 2 or Post-dose 3). Duration and time to onset of AEs will be expressed in days.

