7.2.3. Analysis Methods

Laboratory abnormalities (except CD4+ cell counts in HIV-infected subjects) will be determined in accordance with the toxicity grading tables (Attachment 3 and Attachment 4), and in accordance with the normal ranges of the clinical laboratory. The worst abnormalities following vaccination will be summarized (ie, showing number and percentage) by regimen and presented per period/phase, with special attention to Grade 3 toxicities. Focus will be on clinical abnormalities that occur during Post-dose 1, Post-dose 2 and Post-dose 3 periods, as well as the Regimen Phase. Similar tables for worst abnormalities will be provided pooled by vaccine (dose). A listing will also be provided for subjects with any abnormal laboratory findings following vaccination. For CD4+ cell counts in HIV-infected subjects, a listing will also be generated.

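### SAP Table 2 counts the third-dose period in the Regimen phase, so at the final analysis the 28- and 56-day schedules in Cohort 1 carry third-dose unsolicited AEs and laboratory abnormalities that the 84-day schedule cannot have

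*SAP*

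**What the plan says.** **Definition.** SAP 2.1, Table 2 sets a period after each dose. The third ends at the latest at "23:59 on the date of relative Day 29 Post-dose 3". Note 1 then says: "Regimen period includes both the Post-dose 1, Post-dose 2 and Post-dose 3 periods".

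**Use.** SAP 7 analyses safety on the full analysis set, by cohort and vaccination schedule, and states: "Focus will be on safety signals detected during the Post-dose 1, Post-dose 2 and Post-dose 3 periods, as well as the Regimen phase". SAP 7.1.3 adds that "the AEs following vaccination will be summarized (ie, tables of descriptive statistics) by vaccination schedule and presented per period/phase". For laboratory data, SAP 7.2.3 says: "Focus will be on clinical abnormalities that occur during Post-dose 1, Post-dose 2 and Post-dose 3 periods, as well as the Regimen Phase".

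**Who can have Dose 3.** Protocol 3.1 limits the substudy to about 90 consenting subjects at certain sites in Cohort 1, Groups 1 and 2. It leaves out anyone whose boost was late or missed because of the study pause.

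**Endpoints.** The primary objective (Protocol 2.1) concerns prime-boost schedules of two doses. In Protocol 11.1.1 the AE endpoint is "Adverse events, collected until the 42-day post-last vaccination (excluding third vaccination) visit". The solicited-event endpoint is "Solicited local and systemic adverse events (reactogenicity), collected until 7 days after each study vaccine administration", with no such exclusion. Protocol 11.1.2 lists as a secondary substudy endpoint: "Adverse events, collected from the day of the third vaccination onwards until 28 days thereafter".

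**The concern.** A percentage labelled as the 28-day or 56-day regimen would mix subjects observed after two doses with subjects observed after three. The 84-day row in the same table would hold two-dose observation at most. The extra observation raises the first two rows even if the schedules have the same true risk, and a larger sample would not remove that.

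The added subjects are also selected: they come from certain sites, gave further consent, and missed no boost through the pause. For laboratory data, baseline stays the last value before the prime (SAP 2), and an abnormality counts if it is worse than that baseline (SAP 7.2.1). A Day 8 sample taken after a third dose at 12 to 15 months (Protocol Table 6) would therefore set the worst grade of a prime-boost regimen against a baseline more than a year old.

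Protocol 11 says the primary analysis is meant to help judge which schedule is the best candidate, so rows by schedule will be read against each other.

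**Working it through.** **Passages side by side.** The protocol makes third-dose AEs a secondary endpoint and promises summaries for third-dose recipients (11.5). The SAP supplies a Post-dose 3 period for this, but also folds that period into Regimen. SAP 3, which lists departures from the planned analysis, mentions only the immunogenicity and per protocol sets, so the merger is not declared as a change.

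**Solicited events.** SAP 7 lists reactogenicity after every vaccination, and SAP 7.1.3 measures onset from the start of Post-dose 1, 2 or 3. Attachment 1 allocates solicited events only to Post-dose 1 or Post-dose 2. The route of third-dose solicited events is therefore unresolved. For unsolicited AEs (allocated by start date) and laboratory values there is no such doubt.

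**Inputs.** The plan gives no figure for the Regimen phase to reproduce. The planned sizes add up: 264 + 264 + 132 = 660 in Cohort 1, and 660 + 6 × 66 = 1,056 overall. The share with Dose 3 is f = 90/528 = 17.0% if the 90 split evenly between Groups 1 and 2, and f = 90/264 = 34.1% of one group if all come from it. Nothing in the documents fixes the split. Among active subjects the even-split share is the same: 90 × 5/6 = 75 of 440.

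**Observation time.** Two doses give 2 × 28 = 56 Regimen days and three give 84. The even-split mean in Groups 1 and 2 is 56 + 0.170 × 28 = 60.8 days, or +8.5%. This assumes everyone was boosted.

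**Percentages.** Assume a risk p per dose, equal and independent across doses; p is an assumption, because the documents give no per-dose rates for this population.

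- Two-dose Regimen: 1 − (1 − p)²
- Regimen as written: (1 − f)[1 − (1 − p)²] + f[1 − (1 − p)³]
- Difference: f·p·(1 − p)², largest at p = 1/3, where it equals f × 4/27

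| p per dose | Two-dose | As written, even split | As written, all from one group |
|---|---|---|---|
| 1% | 1.99% | 2.16% | 2.32% |
| 5% | 9.75% | 10.52% | 11.29% |
| 10% | 19.00% | 20.38% | 21.76% |
| 33.3% | 55.56% | 58.08% | 60.61% |
| 70% | 91.00% | 92.07% | 93.15% |

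The largest shifts are 0.170 × 4/27 = 2.5 points and 0.341 × 4/27 = 5.1 points. For rare events the relative excess tends to f/2: 8.5% or 17%. In Group 3 the shift is zero.

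**In subjects.** With 220 active subjects and an even split, p = 10% gives 220 × 0.0138, about 3 extra subjects with an event; p = 1% gives 220 × 0.0017, about 0.4.

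**Sensitivity to equal risk.** If an event followed only Ad26.ZEBOV doses (prime and third, none after the boost), the difference would be f·p·(1 − p). With an even split that is at most 0.170/4 = 4.3 points, and close to 17% relative for rare events.

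**The case against.** **What stands.** The SAP already defines Post-dose 3 as a period that only Dose 3 recipients have. The Post-dose 1 and Post-dose 2 tables are untouched, and schedules can be compared on them. No formal safety test is planned. The randomised contrast of active against placebo within a schedule is kept, because placebo subjects in the substudy receive a third placebo injection. The shift is small beside the sampling error of 220 active subjects. Regimen exposure also varies already: subjects primed before the pause and never boosted stay in their randomised group with no Post-dose 2 period, so the 56-day reference is idealised.

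**Stronger readings that a reader might infer, and that the documents do not support.**

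- That Regimen is the headline summary for comparing schedules. The SAP names it after the three per-dose periods and gives it no higher rank.
- That a headache after Dose 3 is bound to be counted against the 28-day regimen. Headache is solicited, and Attachment 1 may keep third-dose solicited events out of Regimen.
- That every primary safety endpoint excludes Dose 3. The exclusion is attached to the AE endpoint only. Solicited events are collected after each dose, SAEs and IREs run to the end of the study, and laboratory values are not a listed primary endpoint.
- That the comparison with Cohorts 2a, 2b and 3 is spoiled. The SAP evaluates cohorts separately.

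None of this supplies a reason for a two-dose schedule summary to contain a third dose.

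**Conclusion.** The point holds, with a modest effect. As written, the Regimen phase for Groups 1 and 2 of Cohort 1 is a mixture of two- and three-dose observation. It matches neither the two-dose primary objective nor the primary AE endpoint. The direction is known: upward for the 28- and 56-day schedules, with no change for the 84-day schedule. This is established for unsolicited AEs and worst laboratory grade, and open for solicited events until Attachment 1 is reconciled with SAP 7.

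The size limits of about 2.5 points (even split) and 5 points (all from one group) rest on independent doses, equal risk per dose and the planned numbers. They would be larger for events specific to Ad26.ZEBOV. The effect applies at the final analysis. At the Cohort 1 analysis after the 6-month post-boost visit it depends on how many third doses fall before the data cut-off, which the documents do not state.

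**What to change.** 1. In SAP Table 2 Note 1, define Regimen as Post-dose 1 plus Post-dose 2 for every cohort and schedule.
2. Keep Post-dose 3 as its own period, with Dose 3 recipients as the denominator.
3. If a three-dose total is wanted, give it for substudy subjects only.
4. Amend Attachment 1 so that third-dose solicited events are allocated to Post-dose 3.

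The cost is a line of definition, an aligned sentence in Attachment 1 and one phase flag in the analysis datasets; no new data are needed. The change does not settle a separate difference: each SAP period stops at relative Day 29, while the primary AE endpoint runs to 42 days after the last main-study vaccination.

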2.2. Pooling Algorithm for Analysis Centers

There are multiple sites in this study and data from the various sites will be pooled for analysis.

2.3. Analysis Sets

Full Analysis Set

The full analysis set includes all subjects who were randomized and received at least 1 dose of study vaccine (Ad26.ZEBOV, MVA-BN-Filo or placebo), regardless of the occurrence of protocol deviations.

Immunogenicity Analysis Set

The immunogenicity analysis set includes all randomized and vaccinated subjects, who had at least 1 post-vaccination (ie, after the date of vaccination) evaluable immunogenicity sample.

Per Protocol Analysis Set

The per protocol analysis set for the main study includes all randomized and vaccinated subjects, who received both the prime and boost vaccinations (administered within the protocol-defined visit window), have at least 1 post-vaccination (ie, after the date of vaccination) evaluable immunogenicity sample, and have no major protocol violations influencing the immune response. Similarly, the per protocol analysis set for the substudy includes all subjects in the per protocol set for the main study who received the 3rd vaccination and have at least 1 post 3rd vaccination (ie, after the date of vaccination) evaluable immunogenicity sample, and have no major protocol violations influencing the immune response.

The primary immunogenicity analysis will be performed on the per protocol analysis set. Additionally, the analysis will be repeated on the immunogenicity analysis set. For subjects who received Dose 1 (ie, only prime vaccination) but not Dose 2 (or Dose 3) while still continuing their planned visit schedule, the immune response measurements after the planned (ie, upper limit of the analysis visit window that covers the target day for the boost vaccination) but not administered dose 2 will not be included in graphs and tables showing descriptive statistics. These measurements will however be shown in listings, together with the indication that they are not used in the analysis.

It is important to note that vaccination was halted in the Ebola program following a case of Miller Fisher syndrome after receipt of MVA-BN-Filo or placebo. Therefore, there were delays

in scheduled boost vaccinations for some subjects in Cohort 1. A sensitivity analysis will be performed on Cohort 1 to investigate the impact of late boost vaccination on the immune response. For this sensitivity analysis, subjects will be categorized according to the actual Ad26.ZEBOV prime/MVA-BN-Filo boost interval as shown in [Table 3](#).

Further, some subjects in the substudy received the 3rd vaccination within 30 days after Day 365 (post-prime) whereas others received it beyond 30 days after Day 365 (post-prime). Therefore, another sensitivity analysis will be performed to investigate the robustness of receiving the 3rd vaccination within 30 days after Day 365 (post-prime) contrasted with receiving 3rd vaccination beyond 30 days after Day 365 (post-prime).

Table 3: Vaccination Schedules for Sensitivity Analysis

Group	Group Label (Ad26.ZEBOV, MVA-BN-Filo)	Window (Days)
A	28-day interval	[14; 42]
B	56-day interval	[43; 70]
C	84-day interval	[71; 98]
D	140-day interval	[99; 168]
E	196-day interval	[169; 224]
F	252-day interval	[225; 280]
G	≥281-day interval	≥281

Note: The day of the prime vaccination is Day 1.

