## **2. OBJECTIVES AND HYPOTHESIS**

### **2.1. Objectives**

#### **Primary Objective**

The primary objective is to assess the safety and tolerability of different vaccination schedules of Ad26.ZEBOV and MVA-BN-Filo administered IM as heterologous prime-boost regimens on Days 1 and 29, Days 1 and 57, or Days 1 and 85, in healthy adults, including elderly subjects, and on Days 1 and 29 and Days 1 and 57 in HIV-infected subjects and healthy children in 2 age strata.

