### 11.3. Analysis Sets

The Full Analysis set includes all subjects who were randomized and received at least one dose of study vaccine, regardless of the occurrence of protocol deviations. Safety data will be analyzed based on the Full Analysis set.

The Immune Response Analysis set includes all randomized and vaccinated subjects, who have data from baseline and at least one post-vaccination immunogenicity blood draw.

The Per Protocol Analysis set for the main study includes all randomized and vaccinated subjects, who received both the prime and boost (administered not more than 10 days outside the visit window) vaccinations, have immunogenicity data from baseline and at least one post-vaccination evaluable immunogenicity sample, and have no major protocol violations influencing the immune response.

A similar Per Protocol Analysis set will be used for the Cohort 1 substudy for the time points after the third vaccination.

The immunogenicity analysis will be based on the Per Protocol Analysis set. As sensitivity analysis, the immunogenicity data will also be analyzed based on the Immune Response Analysis set, provided more than 10% of subjects in the Immune Response Analysis set are excluded from the Per Protocol Analysis set.

Details on how to handle the data from subjects with a late boost will be described in the SAP, developed before unblinding.

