2.4. Definition of Subgroups

There are 4 cohorts in this study. Subject information and safety data will be analyzed per cohort and vaccination schedule. The immunogenicity data will be presented per cohort (as shown in [Table 4](#)) and vaccination schedule. Only for Cohort 1, ELISA [units/mL] will also be presented by age stratum (aged ≤50 years and aged >50 years).

Table 4: Cohort, Age Group Combinations and Parameters

Cohort	Age Group	Analysis Parameters
1	≥18 years	
 - ELISA (units/mL) - VNA (IC₅₀ titers) - ELISpot - ICS - Ad26 VNA
	≤50 years	ELISA (units/mL)
	>50 years	
2a	18-50 years	
 - ELISA (units/mL) - VNA (IC₅₀ titers) - ELISpot - ICS - Ad26 VNA
2b	12-17 years	- ELISA (units/mL)

		
 - VNA (IC₅₀ titers) - ELISpot - ICS - Ad26 VNA
3	4-11 years	
 - ELISA (units/mL) - VNA (IC₅₀ titers) - ELISpot - ICS - Ad26 VNA

Ad26: adenovirus serotype 26 (vector); ELISA: enzyme-linked immunosorbent assay

ELISpot: enzyme-linked immunospot; IC₅₀: 50% inhibitory concentration; ICS: intracellular cytokine staining;
VNA: virus neutralization assay;

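### In Cohort 1, late boosts are examined by actual interval for immune response only, so Post-dose 2 and Regimen safety by schedule do not separate in-window from late boosts

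*SAP*

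**What the plan says.** Protocol Section 2.1 makes safety by schedule the main question: "The primary objective is to assess the safety and tolerability of different vaccination schedules". Section 11.1.1 lists unsolicited, serious, immediate reportable and solicited events as the primary endpoints. Sections 11 and 11.3 both leave late boosts to the SAP: "Details on how to handle the data from subjects with a late boost will be described in the SAP, developed before unblinding". Neither limits that to immunogenicity, and Section 11.6 repeats the deferral separately for immunogenicity.

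The SAP deals with late boosts in two places, both about immune response:

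- Section 2.3: "A sensitivity analysis will be performed on Cohort 1 to investigate the impact of late boost vaccination on the immune response". It continues: "For this sensitivity analysis, subjects will be categorized according to the actual Ad26.ZEBOV prime/MVA-BN-Filo boost interval as shown in" Table 3, which defines groups A to G, the last starting at Day 281.
- Section 3 removes out-of-window boosts from the per protocol set, which serves immunogenicity only.

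For safety, Section 7 states: "The safety and tolerability data will be summarized based on the full analysis set". That set keeps every randomized and vaccinated subject "regardless of the occurrence of protocol deviations". Section 2.4 adds: "Subject information and safety data will be analyzed per cohort and vaccination schedule", and Section 7 repeats: "Within each cohort, the data will be presented by vaccination schedule". Section 7.1.3 adds tables pooled by vaccine dose, which ignore the interval. SAP Table 2 starts the Post-dose 2 period at the actual second dose. Section 7 has no table, subgroup or sensitivity analysis by prime-boost interval.

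**The concern.** The schedules differ only in the timing of the boost. A Post-dose 2 column headed with a 28-, 56- or 84-day schedule should describe boosts given at about that interval. The protocol allows ±3 days (Table 3, Section 9.1.1), while the SAP provides for boosts as late as Day 281 and beyond. The SAP treats that departure as serious enough to redefine the analysis set for the secondary endpoint, but adds no check for the primary one.

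At stake is the reading of Cohort 1 tolerability by schedule. Protocol Section 11 says the primary analysis is to help judge which schedule to take forward. If late boosts are more or less reactogenic, the columns describe a blend of intervals, and no planned summary would show it.

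**Working it through.** **1. The plan's own precision figures.** Protocol Section 11.2 gives the one-sided 97.5% upper limit when an event is not seen. With 1 − 0.025^(1/n), n = 220 gives 1.66% (stated: below 1.7%) and n = 110 gives 3.30% (stated: below 3.3%). Both reproduce. These are the planned active group sizes per schedule in Cohort 1.

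**2. How late a boost could be.** SAP Table 3 counts the prime as Day 1, so delay = (day − 1) − planned interval.

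| Table 3 group | Days | 28-day schedule | 56-day schedule | 84-day schedule |
|---|---|---|---|---|
| D | 99–168 | 70–139 days late | 42–111 | 14–83 |
| E | 169–224 | 140–195 | 112–167 | 84–139 |
| F | 225–280 | 196–251 | 168–223 | 140–195 |
| G | ≥281 | ≥252 | ≥224 | ≥196 |

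So the SAP's own categories allow for boosts that are months late.

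**3. Where a late boost falls in the safety tables.** The SAP does not say whether schedule means as randomized or as received.

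- *As randomized.* The late boost is counted in the planned column with the in-window boosts. This is the likelier reading. SAP Section 2 assigns prime-only subjects by randomized group, its actual-treatment rule concerns the product given, and the actual schedule is mentioned only for a disposition listing (Section 5.1).
- *As received.* Only three schedules are defined outside the sensitivity analysis, so a boost in groups D to G has no safety column.

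Neither reading gives a safety summary that separates in-window from late boosts.

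**4. What is affected.** The Post-dose 2 period runs from the actual second dose to relative Day 29, so events after a late boost are timed correctly. The issue is which column they enter. The Regimen summary includes Post-dose 2 and inherits it. The Post-dose 1 period ends by relative Day 29 or just before the second dose, so it is largely untouched. The SAP places the delays in Cohort 1 only.

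**5. Size.** Let m be the late share of a column. Then

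column rate − in-window rate = m × (late rate − in-window rate).

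The documents give neither m nor the rates, so all of the following are assumptions.

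| m (assumed) | Shift for a 10-point difference | Shift for 5% in window, 10% late |
|---|---|---|
| 5% | 0.5 points | 0.25 |
| 10% | 1.0 | 0.5 |
| 20% | 2.0 | 1.0 |
| 30% | 3.0 | 1.5 |
| 40% | 4.0 | 2.0 |

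For scale, a 5% rate at n = 220 has a 95% half-width of 1.96 × √(0.05 × 0.95 / 220) = 2.9 points.

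**6. Precision after a split.** Zero-event limits over the same range of m:

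| Planned n | In-window n | Limit | Late n | Limit |
|---|---|---|---|---|
| 220 | 209 to 132 | 1.75% to 2.76% | 11 to 88 | 28.5% to 4.1% |
| 110 | 104 to 66 | 3.48% to 5.44% | 6 to 44 | 45.9% to 8.0% |

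The in-window columns stay informative. The late columns may be thin.

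**The case against.** The strongest reply is that safety handling is specified. Analysing everyone vaccinated, whatever the deviations, follows Protocol Section 11.3. It keeps every exposed subject and preserves the randomized comparison. A late group is formed after randomization and is partly self-selected, because subjects chose whether to take a late boost and signed a specific consent (Protocol Section 9.1.6). The SAP's reason for removing out-of-window boosts, an expected difference in response level, is stated for immunogenicity only. The documents give no reason to expect a different reactogenicity, and on modest assumptions the shift is within sampling error. All of this stands. It supports keeping the full analysis set as the main analysis and labelling any split descriptive. It does not explain why the primary endpoint has no in-window view.

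Three stronger readings may tempt a reader, and the documents do not support them:

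- *About 30% of Cohort 1 was boosted late (200/660).* The protocol's figure of more than 200 affected people is a floor, includes those still awaiting the prime, and is divided here by planned enrolment. It neither counts nor bounds late boosts, and the share may differ by schedule.
- *The trial cannot report tolerability of a late boost.* All adverse events are listed, the actual schedule is listed, and serious, immediate reportable and related Grade 3 events get narratives. What is missing is a pre-specified summary.
- *The primary endpoint as a whole is compromised.* Only part of it is affected, in one cohort.

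It is also fair that SAP Table 3 cannot simply be reused. Group A spans Days 14 to 42, a 28-day subject boosted at Day 60 would join group B, and the groups are defined for the active vaccines only.

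**Conclusion.** The point holds within limits. For Cohort 1, the SAP examines late boosts by actual interval for immune response and not for Post-dose 2 or Regimen safety, which are part of the primary endpoint. The protocol had left late-boost handling to the SAP without restricting it to immunogenicity. Late boosts are therefore tabulated with in-window boosts or, if schedule means as received, those from Day 99 onward lack a column.

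The size of any distortion cannot be derived. It is the late share times a difference in event rates, and the documents give neither; the 0.5 to 4 points above rests on an assumed 5% to 40% share and an assumed 10-point difference. It could be zero if the interval does not affect tolerability. With no formal safety testing planned, no inference is invalidated. The consequence is that the descriptive rates used to weigh the schedules may not describe the schedules as defined, and the reader could not tell.

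**What to change.** In SAP Section 7:

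- Keep the full analysis set tables as the main safety analysis, and state whether schedule is as randomized or as received.
- For Cohort 1, add Post-dose 2 and Regimen tables of solicited and unsolicited adverse events by schedule, split into boost within the protocol-defined window versus late, for active and placebo. Base the split on the actual interval between Dose 1 and Dose 2, so that it also applies to placebo. Use the same window as the per protocol set, and say how boosts postponed under Protocol Section 6.2 are classed.
- Report the number of late boosts per schedule and arm.
- Optionally, break down late active boosts by Table 3 groups D to G, pooling where cells are small.
- Label the split descriptive, noting that the late group is post-randomization and partly self-selected.

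The cost is a few extra tables. No data collection or conduct changes, because vaccination dates are already recorded. The drawback is small late cells, especially in placebo, where 44, 44 and 22 subjects are planned across the three schedules before any split.
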